6.3.11 Stored Plasma and Serum for batched testing for biomarkers

Stored plasma and serum will be collected at the indicated visits (section 6.1) for centralized, batched testing at the UCLA Clinical and Translational Research Laboratory (CTRL) for the following biomarkers: hsCRP, fasting glucose, fasting insulin, fasting lipid panel, hsCRP, sICAM-1, sE-selectin, Lp-PLA2, IL-6, and D-dimer. Fasting glucose and fasting insulin will be performed for non-diabetic subjects only. Subjects must be fasting at least 8 hours (nothing by mouth except medications and water). If subjects indicate a non-fasting state, they should be asked to return in a fasting state within the required visit window (please refer to section 6.1 for more information regarding visit window). If that is not possible, a non-fasting specimen should be obtained the same day, and the non-fasting state should be recorded on the CRF. Stored plasma will be collected at the indicated visits (section 6.1) for centralized testing for endothelial, monocyte, and T-cell microparticles in the laboratory of [name] (UCLA Division of Infectious Diseases). Samples should be collected, processed, and stored on-site frozen at -70°C until shipped to UCLA-WW in accordance with the CTSI-PLACE Study Lab Processing Chart (LPC) (Appendix II). **Subjects should not have received vaccines within 14 days prior to plasma and serum collection.**

6.3.12 Stored Plasma and Serum for future studies

Stored plasma and serum will be collected and processed at the indicated visits (section 6.1) for future studies. Samples will be temporarily stored on site at -70°C until transfer to UCLA-WW for central long-term storage. Samples should be transferred to UCLA-WW every 1-2 months.

prescribed or recreational stimulant use for 24 hours; vigorous exercise for 12 hours.
Subjects should not have received vaccines within 14 days prior to PAT testing.

7.0 CLINICAL MANAGEMENT ISSUES

No clinical management issues are expected as no treatment is being provided in this study.

7.1 Toxicity

No toxicities are anticipated as no treatment or invasive procedures are being performed as part of this study.

7.2 Pregnancy

Pregnancy is not a contraindication to PAT or laboratory testing, but may affect measurements of endothelial function. Pregnancy status should be documented at each PAT visit for female subjects (week 0 and week 52 or 4 weeks after EOT for those with treated HCV).

8.0 CRITERIA FOR DISCONTINUATION

8.1 Premature/Permanent Study Discontinuation

- Request by the subject to withdraw.
- Request of the primary care provider if s/he thinks the study is no longer in the best interest of the subject.
- Subject judged by the investigator to be at significant risk of failing to comply with the provisions of the protocol as to interfere with the validity of the study results.
- At the discretion of the institutional review board (IRB), Office for Human Research Protections (OHRP), investigator, or sponsors.

9.0 STATISTICAL CONSIDERATIONS

9.1 General Design Issues

The CTSI-PLACE Study consists of single-arm evaluation to assess endothelial function cross-sectionally and longitudinally in two study populations: HIV/HCV coinfecting (Group A), a subset of which will undergo HCV treatment, and HIV monoinfected (Group B). The primary endpoint is endothelial function measured by peripheral arterial tonometry reactive hyperemia index (RHI) in both groups.

9.2 Endpoints

9.2.1 Primary Endpoints

9.2.1.1 Reactive hyperemia index (RHI) by PAT at baseline.

9.2.2 Secondary Endpoints

9.2.2.1 Insulin resistance by HOMA-IR (fasting insulin ($\mu\text{U/mL}$) x fasting glucose (mg/dl)/405) at baseline and week 52.

9.2.2.2 Framingham risk score for 10-year CHD and 10-year CVD risk at baseline and week 52.

9.2.2.3 Cardiovascular biomarkers (fasting lipid panel, hsCRP, IL-6, D-dimer, sICAM-1, sE-selectin, Lp-PLA2) at baseline and week 52.

9.2.2.4 RHI by PAT at week 52

9.2.2.5 Change in RHI , biomarkers, HOMA-IR, and FRS from baseline to week 52.

9.3 Sample Size and Accrual

9.3.1 The primary comparison is of baseline RHI between the HIV/HCV coinfecting and HIV monoinfected groups. The estimated difference in RHI between the 2 groups is assumed to be the difference between high-risk CVD (HIV/HCV) and moderate-risk CVD (HIV). RHI is expected then to be 1.6 in HIV/HCV and 1.3 in HIV, with standard deviation (SD) of 0.37.⁵² With a sample size of 80 HIV/HCV and 40 HIV, we have an estimated power of 99% for detection of the expected difference in RHI between the HIV/HCV and HIV groups. However, if we conservatively estimate the difference in baseline RHI to be 0.2 between the 2 groups, we will have 80% power with this sample size. For select secondary analyses of differences in the CVD biomarkers of sICAM-1 (expected difference of 779 vs 1284 ng/mL, SD=526) and sE-selectin (118 vs 223 ng/mL, SD=190),³⁰ we will have 99% and 81% power, respectively, with this sample size.

Accrual of about 20 subjects per month is expected, to complete enrollment in 6 months.

9.3.2 With 80 HCV/HIV subjects, we will have 80% power to detect a correlation between any one marker and RHI of > 0.31 . With 40 HIV subjects, we will have 80% power to detect a correlation > 0.42 , correlations that have been seen in other populations.^{53,54}

9.3.3 Among 80 HIV/HCV subjects, we expect about 40 (50%) will initiate HCV treatment. Out of 40 who initiate HCV treatment, we expect about 27 (67%) will be responders and 13 will be non-responders. To compare responders (n=27) with subjects without treatment (n=40), we will have 80% power to detect a difference of 0.7 in effect size. To compare HIV monoinfected controls (n=40)

and untreated HIV/HCV subjects, we will have 80% power to detect a difference of 0.63 in effect size.

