hsCRP	high-sensitivity C-reactive protein
IATA	International Air Transport Association
ICF	informed consent form
ICH	International Conference on Harmonisation
IFN	interferon
IL-6	interleukin-6
INR	international normalized ratio
IRB	institutional review board
LAB	LA Biomed/Harbor-UCLA
LDL	low-density lipoprotein cholesterol
LPC	Laboratory Processing Chart
Lp-PLA2	lipoprotein-associated phospholipase A2
NIH	National Institutes of Health
OHRP	Office for Human Research Protections
OI	opportunistic infection
PAT	peripheral arterial tonometry
PEG-IFN	pegylated interferon

RBV	ribavirin
RHI	reactive hyperemia index
RNA	ribonucleic acid
SAE	serious adverse event
sICAM-1	soluble ICAM-1
sP-selectin	soluble P-selectin
SVR	sustained virologic response
TC	total cholesterol
TG	triglycerides
WBC	white blood cell
UCLA-WW	UCLA-Westwood

SCHEMA

Clinical and Translational Science Institute Prospective Longitudinal Assessment of Coinfected Subjects with HIV/Hepatitis C for Endothelial Function Study (CTSI-PLACE Study)

DESIGN	Prospective, observational, longitudinal cohort of HIV/HCV coinfecting subjects matched to HIV monoinfected controls with primary cross-sectional analysis of baseline endothelial function and circulating cardiovascular biomarkers.
DURATION	Subjects will be on study for a minimum of 52 weeks. Those who initiate HCV treatment will be on study for at least 24 weeks after end of HCV treatment.
SAMPLE SIZE	A total of 120 subjects will be enrolled in the study (80 HIV/HCV coinfecting and 40 HIV monoinfected subjects).
POPULATION	Group A: 80 HIV/HCV coinfecting subjects Group B: 40 HIV monoinfected subjects All subjects ≥ 18 years of age without known CVD at baseline with CD4 cell count ≥ 200 cells/mm ³ and HIV-1 RNA < 50 copies/mL within 120 days of study entry and on stable antiretroviral therapy (ART) since the time of last CD4 and HIV-1 RNA measurement. Those with a HCV infection must have HCV RNA $\geq 10,000$ IU/mL. The two groups will be frequency matched based upon age, race, sex, diabetes, smoking status, hormonal therapy and statin use, and CD4 cell count at baseline.

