6.2.4 Discontinuation Evaluations

Evaluations for Registered Subjects Who Do Not Start Study Procedures

All CRFs must be completed and keyed for the period up to and including week 0.

Subjects who discontinue the study prior to 1 year

Subjects who permanently discontinue study prior to 1 year and have been enrolled for at least 3 months will have a study discontinuation visit including

repeat biomarker and PAT testing. Subjects on study for < 3 months should be contacted by phone for a telephone interview and have medical record review and data abstraction for clinical events, including new diagnoses and change in medications, since the time of study entry.

Pregnancy

Female subjects who conceive after study entry will be discontinued from the study.

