9.4 Data Analysis Plan

9.4.1 Objective: To determine the effect of HCV coinfection on endothelial function in the HIV-1-infected cohort at baseline.

Descriptive statistics, including mean, SD, median, minimum, maximum, and interquartile range, will be provided for the overall cohort, by HCV status, and by PAT performance site for baseline patient characteristics, RHI, CVD biomarkers, HOMA-IR, hemoglobin A1c, and FRS. Histograms and scatter plots will be produced to visually inspect the distributions and pairwise association. Log-transformation as necessary will be done for RHI, if its distribution is found to be skewed. ANOVA (analysis of variance) will be used to compare continuous variables by HCV status and site and Chi-square test will be used to compare categorical variables. All tests will be 2-sided and a p-value less than 0.05 will be considered statistically significant.

Two sample t-test or Wilcoxon rank sum will be performed to compare RHI in the HIV/HCV vs HIV groups. Multiple linear regression analysis will also be carried out to compare RHI in HIV/HCV vs HIV, adjusting for PAT performance site and any differences in baseline characteristics including CD4 nadir and ART type. Subgroup analyses by race/ethnicity and gender will be conducted. Similar analyses will be carried out to compare biomarkers between the HIV/HCV and HIV groups. Given multiple comparisons, in addition to unadjusted p-values, we will report significance according to Benjamini-Hochberg false discovery rate method.⁵⁵

9.4.2 Objective: To assess whether non-hepatic biomarkers of endothelial dysfunction, inflammation, and thrombosis (sICAM-1, sE-selectin, Lp-PLA2, IL-6, and D-dimer) are better correlates of endothelial function than traditional hepatic-derived biomarkers (hsCRP and lipids) in HIV/HCV-coinfected in cross-sectional assessment.

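### The 80% longitudinal power in section 9.3.3 rests on an unstated assumption that every enrolled subject has a usable follow-up PAT

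*Combined protocol and SAP*

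**What the plan says.** The Schema fixes enrolment: "A total of 120 subjects will be enrolled in the study (80 HIV/HCV coinfecting and 40 HIV monoinfected subjects". Section 9.3.3 then divides the coinfected group for the longitudinal work. It starts from "Among 80 HIV/HCV subjects, we expect about 40 (50%) will initiate HCV treatment", and of those 40 "we expect about 27 (67%) will be responders and 13 will be non-responders". Two power statements follow:

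- "To compare responders (n=27) with subjects without treatment (n=40"), "we will have 80% power to detect a difference of 0.7 in effect size".
- For the 40 HIV monoinfected controls against the untreated coinfected subjects, "we will have 80% power to detect a difference of 0.63 in effect size".

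Section 9.4.3 names the outcome for these groups: change in RHI and in biomarkers from baseline to follow-up, compared pairwise by two-sample t-test or Wilcoxon test, with an ANCOVA as well. Follow-up PAT is due at week 52, or 4 weeks after the end of HCV treatment for those treated (sections 6.1 and 6.3.13).

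The protocol also plans for people leaving early. Section 8.1 lists withdrawal by the subject, a request from the primary care provider and expected non-compliance. Section 6.2.4 adds pregnancy. For the earliest leavers the plan is contact without a visit: "Subjects on study for < 3 months should be contacted by phone for a telephone interview", together with record review. Those enrolled for at least 3 months who leave before 1 year are to have a discontinuation visit that includes repeat PAT and biomarkers (sections 6.1, footnote 1, and 6.2.4).

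Section 9.3 states no loss rate. Section 9.4 states no method for missing follow-up.

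**The concern.** A change from baseline needs two PAT tests, the second about a year after the first or shortly after a course of treatment. The group sizes in 9.3.3 are enrolment numbers: 27 + 13 + 40 = 80 coinfected subjects, plus all 40 controls. The power statement therefore treats everyone enrolled as evaluable, while other sections describe how some will leave, and leave one class of leavers with no second PAT.

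The stake is how a null longitudinal result would be read. Change in RHI is a listed secondary endpoint (section 9.2.2.5). The responder comparison bears on the hypothesis that treating HCV improves endothelial function (section 1.1.3). The Rationale says the project is meant to supply preliminary data for further funding. A reader who takes 0.70 and 0.63 SD as the detectable effects would credit the study with more sensitivity than it has if some second measurements are missing.

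**Working it through.** **Inputs.** Group sizes 27, 40 and 40 and standardised differences 0.70 and 0.63 come from section 9.3.3. The significance level comes from section 9.4.1: "All tests will be 2-sided and a p-value less than 0.05 will be considered statistically significant". The test is the two-sample t-test of section 9.4.3. Section 9.3.3 gives no SD for change, so effects stay in SD units.

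**Formula.** With difference d in SD units, the noncentrality is δ = d × √(n₁n₂/(n₁+n₂)) on n₁+n₂−2 degrees of freedom. Power is the probability that a noncentral t with these parameters exceeds the two-sided 5% critical value in absolute size.

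**Step 1: reproduce the plan, no loss.**

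- 27 vs 40, d = 0.70: δ = 0.70 × √(1080/67) = 2.81, 65 df, power 79.1%.
- 40 vs 40, d = 0.63: δ = 0.63 × √(1600/80) = 2.82, 78 df, power 79.5%.

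The normal approximation gives 80.2% and 80.4%. The effects detectable with 80% power are 0.708 and 0.634 by t. By the normal formula, (1.960 + 0.842) × √(1/n₁ + 1/n₂), they are 0.698 and 0.626. The plan's figures are therefore reproduced, and they use the full enrolled counts.

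**Step 2: allow for missing follow-up.** The documents give no rate, so 5%, 10% and 20% without a usable follow-up PAT are assumptions, applied equally to all groups. Group sizes are rounded to whole subjects (for example 27 × 0.90 = 24.3, taken as 24).

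| Assumed loss | Responders vs untreated | Power at 0.70 | 80%-power effect | Controls vs untreated | Power at 0.63 | 80%-power effect |
|---|---|---|---|---|---|---|
| 0% | 27 vs 40 | 79.1% | 0.71 | 40 vs 40 | 79.5% | 0.63 |
| 5% | 26 vs 38 | 77.3% | 0.72 | 38 vs 38 | 77.4% | 0.65 |
| 10% | 24 vs 36 | 74.3% | 0.75 | 36 vs 36 | 75.1% | 0.67 |
| 20% | 22 vs 32 | 69.9% | 0.79 | 32 vs 32 | 69.9% | 0.71 |

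The choice of formula does not change the picture. By the normal approximation, 5% loss gives 78.5% and 78.4%, 10% gives 75.7% and 76.2%, and 20% gives 71.5% and 71.2%.

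**Step 3: which leavers lose the measurement.** Before 3 months, no repeat PAT is planned. From 3 months to 1 year, a PAT is planned at the discontinuation visit, but three things are open:

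- It is off schedule, and footnote 1 of section 6.1 foresees that it may fall during HCV treatment rather than after it.
- Where pregnancy is the reason for leaving, section 7.2 itself says that pregnancy may affect the measurement.
- Section 9.4.3 does not say whether such a value enters the change analysis.

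The number evaluable therefore cannot be worked out from the plan, even if the discontinuation rate were known.

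**The case against.** The case on the other side is substantial, and most of it limits the size of the point.

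- **The arithmetic is right.** 79.1% and 79.5% round to 80%, and the normal formula slightly exceeds it. A reader might infer a calculation error from the t-based figures. The gap is a matter of formula and rounding, and the documents do not support that reading.
- **Not every leaver loses the outcome.** A reader might also infer that the stated effects cannot be achieved. That does not follow, because the loss rate is unknown and the discontinuation visit would recover some measurements. As an illustration, suppose 10–20% left evenly over a year and only those leaving in the first 3 of 12 months lacked a PAT. Loss would be 2.5–5%, and power (without rounding group sizes) 78.0–76.9% at 0.70 and 78.4–77.3% at 0.63. This stands as a reason for stating the effect conditionally. It does not remove the point: a subject who withdraws may not attend, and the use of the off-schedule value is undefined.
- **Other guesses matter as much.** The 50% uptake and 67% response are approximate. With no loss, 40% uptake (21 vs 48) gives 75.1%, a 57% response (23 vs 40) gives 74.9%, and a 77% response (31 vs 40) gives 82.2%. This is fair, but those assumptions are written down and can err in either direction. The loss assumption is not stated and can err only one way.
- **ANCOVA on baseline may recover precision.** This is true, but no baseline-to-follow-up correlation is given, so the gain cannot be quantified. Section 9.3.3 does not claim it.
- **Only secondary and exploratory comparisons are involved.** This stands in full. The primary endpoint is baseline RHI (section 9.2.1), which later loss cannot affect.

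**Conclusion.** The point holds as an unstated assumption of complete follow-up. Section 9.3.3 has no margin: its 80% is met, to rounding, only when all 27, 40 and 40 subjects have a usable second PAT. At an assumed 10% loss power falls by about 5 points, and at 20% by about 10 points, with detectable effects moving from 0.70 to 0.75–0.79 SD and from 0.63 to 0.67–0.71 SD. These sizes rest on assumed loss rates, equal loss across groups and an unadjusted t-test. The documents fix none of the actual losses, so they support no firmer statement than that the stated power is conditional on follow-up being complete. The effect is moderate and confined to the secondary and exploratory longitudinal comparisons. It is worth correcting because it bears on how a null result would be interpreted.

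**What to change.** In section 9.3.3, state the proportion expected to lack a usable follow-up PAT and give the detectable effects for the number expected to have both tests. For example: assuming 10% without a usable follow-up PAT (24 vs 36 and 36 vs 36), there is 80% power for differences of 0.75 SD (responders vs untreated) and 0.67 SD (controls vs untreated). The team should put in its own rate and give its basis.

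In section 9.4.3, state whether a PAT from the premature discontinuation visit counts as follow-up, including one taken during HCV treatment, so that the evaluable number is defined.

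The cost is wording, with slightly less favourable detectable effects. No change in enrolment is needed. Holding the stated numbers at follow-up would instead require enrolling 120/0.90 = 134 subjects at 10% loss or 120/0.80 = 150 at 20%, which is hard to justify for comparisons that are not primary.

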9.4 Data Analysis Plan

9.4.1 Objective: To determine the effect of HCV coinfection on endothelial function in the HIV-1-infected cohort at baseline.

Descriptive statistics, including mean, SD, median, minimum, maximum, and interquartile range, will be provided for the overall cohort, by HCV status, and by PAT performance site for baseline patient characteristics, RHI, CVD biomarkers, HOMA-IR, hemoglobin A1c, and FRS. Histograms and scatter plots will be produced to visually inspect the distributions and pairwise association. Log-transformation as necessary will be done for RHI, if its distribution is found to be skewed. ANOVA (analysis of variance) will be used to compare continuous variables by HCV status and site and Chi-square test will be used to compare categorical variables. All tests will be 2-sided and a p-value less than 0.05 will be considered statistically significant.

Two sample t-test or Wilcoxon rank sum will be performed to compare RHI in the HIV/HCV vs HIV groups. Multiple linear regression analysis will also be carried out to compare RHI in HIV/HCV vs HIV, adjusting for PAT performance site and any differences in baseline characteristics including CD4 nadir and ART type. Subgroup analyses by race/ethnicity and gender will be conducted. Similar analyses will be carried out to compare biomarkers between the HIV/HCV and HIV groups. Given multiple comparisons, in addition to unadjusted p-values, we will report significance according to Benjamini-Hochberg false discovery rate method.⁵⁵

9.4.2 Objective: To assess whether non-hepatic biomarkers of endothelial dysfunction, inflammation, and thrombosis (sICAM-1, sE-selectin, Lp-PLA2, IL-6, and D-dimer) are better correlates of endothelial function than traditional hepatic-derived biomarkers (hsCRP and lipids) in HIV/HCV-coinfected in cross-sectional assessment.

Correlation analysis (Pearson or Spearman) will be conducted to evaluate the association of each circulating biomarker as the predictor and RHI as a continuous outcome variable. Further correlation of biomarkers with each other and with RHI will be performed by use of correlation matrices. Multiple linear regression models will be used while controlling for confounders as in Aim 1 analysis, but with each biomarker as the primary independent variable to determine the contribution of each biomarker as a predictor of RHI. A final model will be constructed by including all significant biomarkers to predict RHI. The adjusted R-squared value will be used to indicate the predictive ability of the model. Similar analysis will be carried out in HIV-monoinfected subjects only to derive the RHI prediction model. The models for each cohort will be compared to each other for their predictive ability and differences in individual biomarker

significance in each cohort. This analysis will allow us to define whether non-hepatically-derived biomarkers have stronger correlation with RHI than hepatically-derived biomarkers.

9.4.3 Objective: To determine the effect of HCV co-infection and HCV virologic suppression post treatment on endothelial function and CVD biomarkers in the HIV-1-infected cohort over one year of follow-up.

Change in RHI and change in biomarkers from baseline to follow-up will be compared among 4 groups of subjects (HCV treatment responders and non-responders, untreated HIV/HCV subjects, and HIV controls). Boxplots will be used to visually display the difference among 4 groups. Pair-wise comparison will be carried out based on 2-sample t-test or Wilcoxon test. ANCOVA will be carried out to compare among 4 groups adjusting for baseline values and demographic characteristics and other baseline confounders. Adjusted comparison between any 2 groups will be estimated based on appropriate contrast. Correlation analysis will be carried out between change in biomarkers and change in RHI.

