3.0 STUDY DESIGN

This is a prospective, observational, longitudinal study of two groups, Group A, HIV/HCV coinfecting subjects and Group B, HIV monoinfected subjects. The HIV/HCV subjects

will be frequency-matched to the HIV monoinfected subjects by age (<40, 40-49, 50-54, and ≥55 years), race (white, black, other), sex at birth, diabetes (yes/no), smoking status (current or not), HMG Co-A reductase inhibitor (statin) and hormonal therapy use, and CD4 cell count (200-349 and ≥350 cells/mm³) at baseline. All subjects will be followed for a minimum of 1 year. A subset of the HIV/HCV coinfecting group are expected to initiate HCV treatment during this time and will be followed through up to 24 weeks following end of HCV treatment. All subjects will be included in baseline cross-sectional analysis of endothelial function, measured by peripheral arterial tonometry (PAT) and laboratory testing for circulating CVD biomarkers. All subjects will have follow-up PAT and laboratory testing and clinical follow-up. Those HIV/HCV coinfecting that do not begin HCV treatment and all HIV monoinfected will have follow-up PAT and laboratory testing at 1 year. Those HIV/HCV coinfecting who begin HCV treatment will have follow-up PAT and laboratory testing at 4 weeks after end of HCV treatment, but will be followed clinically for up to 24 weeks after end of treatment to capture complete HCV treatment response data.

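### The baseline RHI regression in 9.4.1 fixes none of the eight matching factors as covariates; each enters only if the groups are held to differ on it

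*Combined protocol and SAP*

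**What the plan says.** - Section 3.0: the coinfected subjects "will be frequency-matched to the HIV monoinfected subjects by age", race, sex at birth, diabetes, smoking, statin use, hormonal therapy and CD4 stratum. That is eight factors.
- Section 9.3.1: "The primary comparison is of baseline RHI between the HIV/HCV coinfecting and HIV monoinfected groups". Power is given for 80 versus 40 subjects with SD 0.37 and no covariates: 99% at the expected difference of 0.3 and 80% at the conservative 0.2.
- Section 9.4.1, unadjusted test: "Two sample t-test or Wilcoxon rank sum will be performed to compare RHI in the HIV/HCV vs HIV groups".
- Section 9.4.1, regression, which is additional to that test: "adjusting for PAT performance site and any differences in baseline characteristics including CD4 nadir and ART type". PAT site is unconditional. CD4 nadir and ART type are named and can be read as always included. None of these three is a matching factor.
- Section 9.4.1, baseline comparisons: "ANOVA (analysis of variance) will be used to compare continuous variables by HCV status and site", with chi-square for categorical variables, and "All tests will be 2-sided and a p-value less than 0.05 will be considered statistically significant". Neither sentence is offered as a rule for choosing covariates.
- Section 9.4.2, biomarker models: "Multiple linear regression models will be used while controlling for confounders as in Aim 1 analysis". The same set therefore carries over.
- Section 9.4.3: the follow-up ANCOVA adjusts for demographic characteristics without making this depend on a group difference. The baseline regression has no such provision.

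**The concern.** Matching and adjustment are meant to work together. If age, smoking or diabetes predict RHI, balancing them makes the group difference less variable, but a model that omits them leaves their contribution in the residual. The reported standard error is then too large and the test too cautious.

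The opposite problem arises when matching is imperfect. A rule that reacts to observed differences has little chance of noticing a moderate imbalance with 80 and 40 subjects. A missed imbalance in a factor related to RHI shifts the estimated HCV effect. In an observational comparison this is the main threat, and the Background section itself faults earlier studies for uncontrolled confounding.

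At stake are a few points of power at the conservative difference, and protection against residual confounding in the analysis of objective 1.2.2.

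**Working it through.** **Inputs.** From 9.3.1: n = 80 and 40, SD 0.37, differences 0.2 and 0.3. From 9.4.1: two-sided 0.05. Assumed, because the documents do not give it: the eight factors jointly explain R² = 0.10 to 0.25 of RHI variance, with R² = 0 also shown.

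**1. The plan's own figure.** SE = 0.37 × √(1/80 + 1/40) = 0.0717. Noncentrality at 0.2 is 0.2/0.0717 = 2.79, which on 118 df gives 79.1% power. At 0.3 it is 4.19, giving 98.6%. The stated 80% and 99% reproduce.

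**2. What a p<0.05 screen would detect.** For a continuous factor off by m SD, the noncentrality is m/√0.0375. For m = 0.2 this is 1.03 and the imbalance is flagged 18% of the time; for m = 0.3 it is 1.55 and 34%. For binary factors, exact enumeration of the chi-square test gives 17% for 50% vs 40%, and 33% for 50% vs 35%. A missed imbalance of 0.3 SD in a factor correlated 0.3 with RHI (assumed) shifts the difference by 0.3 × 0.3 × 0.37 = 0.033, or 17% of 0.2.

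**3. Cost in degrees of freedom.** HCV 1, site 1, nadir 1, ART 1 (two classes), age 1, race 2, five binary factors 5, CD4 1: 13 in total. Residual df = 120 − 1 − 13 = 106. Using the matching bands for age and CD4 gives 15. In the n = 40 model of 9.4.2, the 12 terms other than HCV plus one biomarker leave 40 − 1 − 12 − 1 = 26.

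**4. Power of the fixed set, analytically.** Residual SD = 0.37 × √(1 − R²), on 106 df. With exact balance at 0.2, power is 79%, 83%, 85% and 89% for R² = 0, 0.10, 0.15 and 0.25. With chance imbalance the variance is inflated by 1 + 12/106 = 1.113, and power is 75%, 79%, 81% and 86%.

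**5. Comparison by simulation.** 6,000 runs per setting (Monte Carlo error about 0.5 points), with eight equally weighted factors and binary prevalences of 15–40% (assumed). *Planned* means site, CD4 nadir and ART type plus any matching factor with p<0.05. *Fixed* means the 13-df set. Power at 0.2, in percent:

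| Balance | R² | t-test | Planned | Fixed | Fixed − planned |
|---|---|---|---|---|---|
| Chance | 0 | 79.4 | 77.5 | 74.9 | −2.6 |
| Chance | 0.10 | 78.9 | 77.3 | 79.4 | +2.1 |
| Chance | 0.15 | 79.3 | 78.2 | 81.0 | +2.8 |
| Chance | 0.25 | 78.6 | 78.4 | 85.6 | +7.2 |
| Exact | 0 | 78.8 | 77.9 | 77.8 | −0.1 |
| Exact | 0.10 | 80.6 | 79.6 | 82.5 | +2.9 |
| Exact | 0.15 | 81.0 | 80.5 | 84.8 | +4.3 |
| Exact | 0.25 | 82.1 | 80.9 | 88.0 | +7.1 |

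At a difference of 0.3 with exact balance, every model is at about 99% or above for R² = 0.10–0.25.

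**6. Type I error.** With exact balance the planned model rejects 3.9%, 3.4% and 2.4% of the time at R² = 0.10, 0.15 and 0.25; the fixed set rejects 4.6–5.3%. The estimate varies equally in both models (SD 0.066 at R² = 0.15); only the reported SE differs (0.072 vs 0.067). With imbalances in random directions the planned model stays at 4.6–5.5%. With all eight factors off in the same direction, an illustrative worst case, it rises to 6–7% at 0.1 SD and 9–13% at 0.2 SD, while the fixed set stays near 5%.

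**The case against.** The best reply has four parts.

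- **The p<0.05 rule is inferred.** A reader might take the plan to say that matching factors are dropped whenever matching succeeds at p<0.05. The text does not go that far: it gives no entry criterion, promises descriptive summaries by HCV status from which differences could be gauged by size, and in 9.4.2 calls the set confounders. This stands. The flag rates and the planned-model figures hold only if the screen is at p<0.05. What does not depend on it is that no matching factor is fixed.
- **Exact balance is the favourable case.** The matching categories cross to 4 × 3 × 2⁶ = 768 cells for 120 subjects, so exact joint balance is out of reach. This stands, and the chance-imbalance rows are the fairer guide. There the fixed set roughly breaks even with the t-test at R² = 0.10 (79.4% vs 78.9%).
- **No validity failure under ordinary conditions.** With good matching the planned test errs on the cautious side, and with random-direction imbalance its error rate is near nominal. The 9–13% figure needs all eight factors to lean the same way. This also stands.
- **The remedy has its own cost.** Diabetes is listed in the Background as a possible mechanism of HCV-related risk, and section 5.0.2 accepts all antiretroviral regimens, so ART type could use many df. Both can be handled: matching already conditions on diabetes, so a sentence of justification is enough, and ART can be grouped.

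None of this makes a difference-driven covariate list preferable to a fixed one built from data the study already needs.

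**Conclusion.** The point holds as an inexpensive improvement. Section 9.4.1 leaves all eight matching factors to an unstated judgement about group differences. Replacing that with a fixed set changes power at a difference of 0.2, relative to the planned regression, by about +2 to +7 points with chance imbalance and +3 to +7 with exact balance, and it removes dependence on a screen that would miss most moderate imbalances. These gains assume R² of 0.10–0.25 and a p<0.05 entry rule; neither is in the documents. At R² near zero the sign reverses.

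A reader might go further and conclude that the sample size is wrong, that the planned result would be biased, or that the regression must replace the t-test/Wilcoxon as the primary analysis. The documents support none of these. The stated power reproduces for the unadjusted test. Under exact matching the estimate is unbiased and no less precise. Which analysis is primary is a separate and more debatable question.

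**What to change.** In the 9.4.1 regression, replace the difference-driven wording with a fixed list, included whatever the observed differences: PAT site, age, race, sex, diabetes, smoking, statin use, hormonal therapy, CD4 count, CD4 nadir and ART type grouped into few classes. Add a sentence explaining why diabetes is included. Keep the t-test/Wilcoxon as planned. In 9.4.2, pre-specify a shorter list for the n = 40 monoinfected model, where the full list would leave only 26 residual df.

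**Cost.** No new subjects or data: every covariate is already a matching factor or named in 9.4.1. The model uses about 13 df, more if ART has more than two classes. If the factors explain almost none of the RHI variance and balance is left to chance, power at 0.2 is 2.6 points below the planned regression and 4.5 below the unadjusted test (74.9% vs 79.4%); with the matching bands it is 73.7%, or 5.7 below.
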